#### **From Month 3-12:**

Consideration of alternative therapies, such as PDT, laser, or steroids will be at the investigators discretion but guidelines for alternative therapies are as follows:

Photodynamic therapy with visudyne or laser photocoagulation or intravitreal steroids may be considered as monotherapy or in combination with ranibizumab 2.0mg if the following criteria are met:

- 1. There is a  $\geq 10$  letter visual acuity loss from baseline or from a previous visit and 2 consecutive ranibizumab injections have been performed 1 and 2 months prior to the current visit and there is persistent acitivity on OCT (intraretinal edema, subretinal fluid, pigment epithelial detachment with fluid etc).*

*And for PDT or Laser (not applicable to steroids)*

- 2. There is well defined hyperfluorescence on fluorescein angiography or ICG angiography that the investigator feels would be amenable to PDT or laser therapy.*

#### **Timing of Intervention and Assessments**

#### **Baseline/Day 0 (same day or different days):**

Informed Consent, Medical and Ophthalmic History, Blood Pressure, Manifest Refraction, ETDRS Best Corrected Visual Acuity , IOP, dilated slit lamp examination with biomicroscopy and direct ophthalmologic exam, Routine Physical Exam, Fluorescein/ICG Angiography, OCT, and Fundus Photography, urine pregnancy test (women of childbearing potential only) Administration of 2.0mg Intravitreal Ranibizumab #1

**1wk post treatment safety visit following intravitreal injection of Ranibizumab injection:**

Snellen visual acuity with spectacles or pinhole, intraocular pressure, dilated slit lamp examination with biomicroscopy and indirect ophthalmoscopy, and blood pressure.

**Month 1 & 2:**

Blood Pressure, Manifest Refraction, ETDRS Best Corrected Visual Acuity , IOP, dilated slit lamp examination with biomicroscopy and direct ophthalmologic exam, Fluorescein/ICG Angiography, OCT, and Fundus Photography. Intravitreal 2.0 mg Ranibizumab #2 and #3 respectively.

**Month(s) 3 -12:**

Blood Pressure, Manifest Refraction, ETDRS Best Corrected Visual Acuity, IOP, dilated slit lamp examination with biomicroscopy and direct ophthalmologic exam, Fluorescein/ICG Angiography (mandatory at months 3,6,9,12; optional at other visits), OCT, and Fundus Photography (mandatory at months 3,6,9,12; optional at other visits). Urine pregnancy test at month 12 for females of childbearing potential only.

*From months 3 onward, at the discretion of the Investigator, Intravitreal 2.0 mg Ranibizumab, observation or non-study therapy (i.e. laser, intravitreal steroids, PDT etc.) may be administered. Other anti-VEGF agents including bevacizumab and standard dose (0.5mg) ranibizumab are excluded as optional therapies.*

**Month(s) 18 & 24**

Telephone Interview to assess for adverse events. Subjects will not be eligible to receive 2.0mg Ranbizumab. Alternate treatments are at the investigators discretion during the off drug observational period.

#### **Patient Accrual-**

Subject Accrual per Month:1

Date of First Subject Enrolled: November 1, 2010

Date of Last Subject Enrolled: July 1, 2012

Date of Last Subject Completing Study: July 1, 2013

### **3.2 RATIONALE FOR STUDY DESIGN**

The route (intravitreal injections) and 2.0 mg dose employed is currently evaluated in the HARBOR clinical trial evaluating 2.0 mg Ranibizumab in neovascular AMD. The three consecutive monthly injections will be followed by observation or therapy at the discretion of the investigator. Given the variable course of PCV and unknown response to 2.0 mg Ranibizumab, this regimen will allow the opportunity to evaluate Ranibizumab's safety and potential therapeutic efficacy, as well as to give the patient the opportunity to continue Ranibizumab or switch to an alternative non-anti-VEGF therapy. The 1 year duration of the study is of sufficient duration to determine significant safety issues as well as determine potential efficacy. The possible inclusion of patients completing month 24 follow up after receiving 0.3mg or 0.5 mg doses in our previous study, will determine significant safety issues as well as determine potential efficacy of the 2.0mg dose for this population, as well.

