### **2.0 mg Ranibizumab cohort**

Twenty eyes will be treated; PCV eyes may be treatment naïve or received previous PCV therapy greater than 30 days prior to enrollment. A maximum of 10 eyes that completed 24 month enrollment in our study evaluating 0.3 mg or 0.5mg Ranibizumab may be included. *Eyes will be treated with 3 monthly doses of 2.0 mg ranibizumab followed by 2.0mg ranibizumab on a PRN dosing regimen for 9 months.*

*In the year 2 off drug treatment period subjects will be contacted via telephone interview for review of adverse events at month 18 and month 24.*

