### **3.4 SAFETY PLAN**

The safety assessments to be conducted for this study are listed in Section 4.5 and Appendix A.

Serious adverse events of intravitreal injection such as endophthalmitis, retinal detachment and significant vitreous hemorrhage will be reported and monitored. Potential serious adverse events related to study drug such as significant uveitis, hypertension, thromboembolic event, or poor wound healing will be reported and monitored. Serious ocular adverse events such as major subretinal hemorrhage, vitreous hemorrhage and 6-line loss rate will be reported and monitored. Serious adverse events such as hospitalizations, surgeries, emergency room admissions and death will be reported and monitored.

Given the small population studied in this Phase I trial, it will be difficult to estimate the adverse event occurrences. Unmasking procedures or treatment recommendations related to drug or the study in particular are not necessary. Any death in the study population will lead to review and assessment while withholding drug injections for enrolled patients until fully reviewed. If two or more patients suffer thromboembolic events, drug injections will also be withheld for all enrolled patients until review and assessment occur.

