## 4.8 STATISTICAL METHODS

### 4.8.1 Analysis of the Conduct of the Study

There is no formal sample size calculation in this pilot study. As this is a phase I study, a sample size of 20 patients is chosen, making sure that it is feasible financially to conduct the study and logically to complete the study within 2-3 years. If and when the study is planned for a phase II randomized control trial, appropriate statistical analysis will be determined.

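### Section 3.2 says the prior-study subjects will settle the safety of 2.0 mg, but neither 10 eyes nor all 20 subjects can do that for uncommon serious events

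*Combined protocol and SAP*

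**What the plan says.** Section 3.2 makes two statements about what the study will establish. The first concerns follow-up: "The 1 year duration of the study is of sufficient duration to determine significant safety issues as well as determine potential efficacy". The second concerns subjects who completed 24 months in the sponsor's previous 0.3/0.5 mg study. Their possible inclusion "will determine significant safety issues as well as determine potential efficacy of the 2.0mg dose for this population, as well".

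On numbers, Section 3.1 limits the second group: "A maximum of 10 eyes that completed 24 month enrollment in our study evaluating 0.3 mg or 0.5mg Ranibizumab may be included". Section 4.8.1 says "There is no formal sample size calculation in this pilot study" and that "a sample size of 20 patients is chosen, making sure that it is feasible financially to conduct the study". Section 3.1 describes an open-label, single-centre, uncontrolled case series.

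On precision, Section 3.4 says: "Given the small population studied in this Phase I trial, it will be difficult to estimate the adverse event occurrences". Section 4.8.2 plans a summary of the safety data, and Section 4.8.3 plans percentages of enrolled patients. Neither gives a confidence interval or an event rate that the study could detect.

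**The concern.** The incidence and severity of adverse events is the primary outcome (Section 3.3.1), so the rationale's account of what the study can show about safety bears on its main result. The sentence on prior-study subjects makes an unqualified promise about the smallest group in the study.

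That promise also has no stated analysis behind it. No separate summary of these subjects is planned, and prior-study status is not among the variables Section 4.8.3 names (its list is open-ended). Sections 4.1.1 and 4.1.2 let these subjects enter without active exudative disease, so findings in the other subjects do not simply carry over to them.

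What is at stake is how an empty row in the adverse event table is read. If no thromboembolic event or endophthalmitis occurs, a reader who relies on Section 3.2 could take the question as answered for 2.0 mg. With these numbers, no events is the more likely result at the reference rates, and it would exclude little.

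**Working it through.** The plan has no sample-size or precision figure to reproduce. The check is therefore what 20 subjects, or at most 10 prior-study eyes, can show.

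**Inputs**
- n = 20 (Section 4.8.1) and n = 10, the cap in Section 3.1.
- From Section 1.5, for 0.3/0.5 mg: arterial thromboembolic events (ATE) 1.9% in year 1; endophthalmitis or presumed endophthalmitis 0.4% (0.5 mg group of the large safety study); intraocular inflammation and raised pressure as serious events, below 2%; serious injection-procedure events, below 0.1% per injection.
- From Section 1.3, the sponsor's previous series of 20 eyes: 2 mild vitreous hemorrhages (10%) and 3 cataract progressions (15%).

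**Step 1. Chance of at least one event:** 1 − (1 − p)^n

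| Event and true rate p | n = 20 | n = 10 |
|---|---|---|
| Endophthalmitis, 0.4% | 7.7% | 3.9% |
| ATE, 1.9% | 31.9% | 17.5% |
| Serious inflammation or raised pressure, at the 2% ceiling | 33.2% | 18.3% |
| ATE rate doubled, 3.8% | 53.9% | 32.1% |
| Vitreous hemorrhage, 10% | 87.8% | 65.1% |
| Cataract progression, 15% | 96.1% | 80.3% |

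For example, ATE with n = 20 gives 1 − 0.981^20 = 31.9%.

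**Step 2. Injection-procedure events, counted per injection.** At the 0.1% ceiling, 20 eyes with the minimum of 3 injections (60 in all) give 1 − 0.999^60 = 5.8%. With 13 each, Day 0 to Month 12 (260 in all), the result is 1 − 0.999^260 = 22.9%.

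**Step 3. True rate needed for a 95% chance of at least one event:** 1 − 0.05^(1/n)
- n = 20: 13.9%
- n = 10: 25.9%

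**Step 4. Upper limit after zero events, two-sided exact 95%:** 1 − 0.025^(1/n)
- 0/20: 16.8%
- 0/10: 30.8%

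Steps 3 and 4 answer different questions. The first is a detection threshold, and the second is the upper end of a confidence interval.

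**Step 5. One observed event.** The Clopper-Pearson 95% interval is 0.1% to 24.9% for 1/20 and 0.3% to 44.5% for 1/10.

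**Step 6. Size needed for a 95% chance of one ATE at 1.9%:** ln(0.05)/ln(0.981), rounded up, is 157 subjects.

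**The case against.** The strongest reply is that the protocol, read as a whole, does not claim to rule out uncommon events. It calls itself a pilot, says the number was set by feasibility, describes an uncontrolled series and warns in Section 3.4 about the small population. The primary objective is only to investigate safety. All of this is true, and it limits the point to what Section 3.2 asserts.

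Several stronger readings are tempting and are not supported:

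- *The duration sentence makes a sample-size claim.* It is literally about length of follow-up, and nothing computed here tests whether 12 months is long enough. The sentence on prior-study subjects carries the point.
- *Sections 3.2 and 3.4 contradict each other outright.* One speaks of determining safety issues and the other of estimating occurrence. They are in tension, but not opposites.
- *Most of the events the protocol names would go unseen.* This is not shown. Several examples in Section 3.3.1 have no rate in the documents, and vitreous hemorrhage, which is on that list, would probably be seen at the previous series' crude 10%. That series is small, and its mean follow-up was 18 to 19 months.
- *Zero events would be declared safe.* No section sets such a rule. The risk is one of interpretation.

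It can also be said that the ATE figure covers one year while telephone review runs to Month 24. If the 2.6% second-year rate in Section 1.5 is compounded with the first, the two-year risk is 1 − 0.981 × 0.974 = 4.5% and the chance of at least one event in 20 is about 60%. That is an assumption, because year 2 here is off drug. It still leaves about a 40% chance of seeing none, and one case in 20 would have the wide interval shown in Step 5, with no control group to compare.

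**Conclusion.** The point holds for uncommon serious events. Section 3.2 promises that the prior-study subjects will settle safety at 2.0 mg for their population. At the reference rates, 20 subjects have about a one-in-three chance of showing any ATE in year 1 and about a one-in-thirteen chance of showing any endophthalmitis. Ten eyes have roughly half those chances. Events with a true rate of about 14% or more would very likely appear among 20 subjects.

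Choosing 20 subjects for feasibility is not a fault in a Phase I pilot. The fault is the property claimed for that number.

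The figures assume one study eye per subject, independent events and no losses. Losses would weaken them, since Section 4.8.4 analyses available cases. The 0.3/0.5 mg rates, drawn from a programme in neovascular AMD, serve only as reference values because the documents give no rate for 2.0 mg in polypoidal choroidal vasculopathy. Ten is a cap, so the actual prior-study group may be smaller and its limits wider.

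**What to change.** 1. In Section 3.2, keep the duration sentence but confine it to the adequacy of 12 months' follow-up.
2. Replace the sentence on prior-study subjects with wording that agrees with Section 3.4. For example: With 20 subjects there is a 95% chance of seeing at least one case only of events whose true incidence is about 14% or more (about 26% within the prior-study group if 10 eyes are enrolled). If no case is seen, the two-sided exact 95% upper limit is 16.8% for 0/20 and 30.8% for 0/10. The study will not support conclusions about rarer events.
3. In Sections 4.8.2 and 4.8.3, report each primary adverse event incidence with its Clopper-Pearson 95% confidence interval, based on the actual n. State the denominator, since Section 4.8.3 uses patients enrolled and Section 4.8.4 uses available cases. If a statement about the prior-study subjects is kept, give their incidences separately.

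The cost is two sentences and one column in the adverse event table. Treatment, visits and sample size do not change. The drawback for the sponsor is that the stated safety claim becomes less favourable.

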### **3.3 OUTCOME MEASURES**

#### **3.3.1 Primary Outcome Measure**

The primary outcome measure for safety and tolerability is the following:

Incidence and severity of ocular and systemic adverse events. Examples include 30 letter loss, major subretinal hemorrhage, involving 75% or more of clinical macula (arcade to arcade), disease-related vitreous hemorrhage, injection-related endophthalmitis, retinal detachment, vitreous hemorrhage, *study drug/procedure* -

related uveitis, incidence and severity of other adverse events, as identified by physical examination, subject reporting, and changes in vital signs.

### **Secondary Outcome Measures**

- Month 3, 6, 9, 12 best corrected visual acuity at 4 meters – rates for gain of 5,10 and 15 or more letters
- Month 3, 6, 9, 12 best corrected visual acuity at 4 meters- rates for loss of 15 or more letters
- Median and Average best corrected visual acuity at 4 meters- gain/loss (letters) at 3,6,9,12 months.
- Mean change from baseline in central foveal thickness over time up to 12 months as assessed on OCT
- Mean change from baseline in macular volume overtime up to 12 months.
- Proportion of patients with no evidence of fluid from CNV as assessed by OCT at 12 months.
- Mean change from baseline in the total area of CNV fluorescein angiographic leakage overtime up to 12 months.
- Mean change from baseline in total area of ICG CNV lesion size (including polyps and deep choroidal vessels) overtime up to 12 months.
- Fluorescein and ICG angiograms and fundus photographs will also be graded at each time point compared to baseline as unchanged, resolved, improved, worsened, or cannot determine. For the FA and ICG evaluations, “resolved” will be defined as no leakage and no evidence of polyps or PCV choroidal lesion; “improved” will be defined as decreased leakage and/or decreased size, number, or hyperfluorescence of polyps and/or PCV choroidal lesion; and “worsened” will be defined as increased leakage and/or increased size, number or hyperfluorescence of polyps and/or PCV choroidal lesion. For fundus photography evaluations, “resolved” will be defined as no evidence of PED, subretinal fluid, hemorrhage, or hard exudate; improved will be defined as a decrease in PED,

subretinal fluid, hemorrhage, or hard exudate; and “worsened” will be defined increase in PED, subretinal fluid, hemorrhage, fibrosis, or hard exudates.

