## 4. **MATERIALS AND METHODS**

### 4.1 SUBJECTS

#### 4.1.1 **Subject Selection**

Twenty subjects from one site in the United States will be enrolled. Subjects with active, exudative-PCV who have provided informed consent will be eligible. Subjects who completed the 24 month follow up in the original FVF3671s 0.3 mg or 0.5mg PCV protocol may enter the extension study with 2.0 mg without necessarily demonstrating active exudative PCV at enrollment. (See Appendix A, the study flow chart, for screening assessments.)

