#### 4.1.2 **Inclusion Criteria**

Subjects will be eligible if the following criteria are met. *Any deviation/waivers granted regarding inclusion/exclusion criteria will be reviewed by the principal investigator and fully documented.*

- Males and Females >18 years of age. *Females of child bearing potential will undergo urine pregnancy testing* and be required to use appropriate methods of birth control.
- ICG and fluorescein angiographic characteristics consistent with active, leaking PCV with subfoveal lesions &/or subfoveal hemorrhage, lipid exudates, PED or fluid diagnosed within the past 6 months or diagnosed as newly active within the past 6 months. Subjects who completed the 24 month follow up in the original FVF3671s protocol may enter the extension study with 2.0 mg without necessarily demonstrating active exudative PCV at enrollment.
- Best-Corrected ETDRS Visual Acuity at 4 meters between 20/20 – 20/800
- Lesion size- no limitations
- Lesion Characteristics- leaking lesions consistent with PCV. No limitations on hemorrhage, fibrosis or atrophy.
- No therapy (includes non foveal laser, PDT, intravitreal steroids, TTT, radiotherapy, or anti-VEGF therapy) or intraocular surgery within the past 30 days for any condition.

- Clear ocular media to allow for photography/angiography.
- Ability to provide written informed consent and comply with study assessments for the full duration of the study

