#### **4.2 METHOD OF TREATMENT ASSIGNMENT**

This is a non-randomized, open-label study of 2.0 mg Ranibizumab. Treatment assignment will be determined by baseline status of treatment naive vs. previously treated PCV eyes.

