### 4.8.3 Efficacy Analyses

1. **Primary Endpoint-** See Section 3.3.1

2. **Secondary Endpoints-** See Section 3.3.2

All subjects will be used in analysis of primary and secondary outcome parameters. Rates for the endpoints at the suggested time points will be presented as a % of the patients enrolled. Analysis of Variance will be used to assess for role of variables in for the endpoints. Variables will include # Ranibizumab injections, other therapies, baseline acuity, age, gender, etc.

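### The Month 12 no-fluid proportion has no baseline-fluid condition, and up to 10 of 20 eyes may be rollovers admitted without active exudation, so it cannot separate eyes that dried from eyes that stayed dry

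*Combined protocol and SAP*

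**What the plan says.** **Endpoint.** The list of secondary outcome measures (Section 3.3) includes the "Proportion of patients with no evidence of fluid from CNV as assessed by OCT at 12 months". It carries no condition on the baseline scan.

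**Denominator.** Section 4.8.3 uses all subjects for the primary and secondary outcomes and adds: "Rates for the endpoints at the suggested time points will be presented as a % of the patients enrolled". Section 4.8.4 bases analyses on available cases without imputation.

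**Rollovers.** Section 3.1 (2.0 mg cohort) treats twenty eyes and says: "A maximum of 10 eyes that completed 24 month enrollment in our study evaluating 0.3 mg or 0.5mg Ranibizumab may be included". Under Section 4.1.1 subjects who completed that study "may enter the extension study with 2.0 mg without necessarily demonstrating active exudative PCV at enrollment". Section 4.1.2 repeats the waiver inside its activity criterion.

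**Other subjects.** Section 4.1.1 requires active, exudative PCV. Section 4.1.2 requires angiographic features of active, leaking PCV "with subfoveal lesions &/or subfoveal hemorrhage, lipid exudates, PED or fluid diagnosed within the past 6 months". No entry criterion names an OCT finding.

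**Measures referenced to baseline.** These are mean change in OCT central foveal thickness, in macular volume, in fluorescein leakage area and in ICG lesion size. In addition, "Fluorescein and ICG angiograms and fundus photographs will also be graded at each time point compared to baseline". OCT is not among the graded modalities.

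**Subgroups and covariates.** Section 4.2 states: "Treatment assignment will be determined by baseline status of treatment naive vs. previously treated PCV eyes". The variable list in Section 4.8.3 names injections, other therapies, baseline acuity, age and gender and is left open. It names neither baseline fluid nor rollover status.

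**The concern.** An eye that enters with fluid and is dry at Month 12 has changed. An eye that enters dry and is dry at Month 12 has not, but both add one to the numerator. The entry rules let both kinds in, so the pooled rate depends partly on the mix of eyes enrolled.

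This bears on the plan's own aims. Section 1.3 justifies the 2.0 mg dose by lesions that resist standard-dose monotherapy. Section 3.2 says that including earlier-study patients will help determine potential efficacy in that population. Whether wet eyes dried, and how rollovers fared, are the natural questions. The pooled figure answers neither. At stake is the interpretation of one descriptive secondary endpoint.

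**Working it through.** The plan states no expected rate, target or power for this endpoint, so there is no figure to reproduce. The check has two parts.

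**1. Can eyes enter dry on OCT, and does another measure recover the change?**

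- *Rollovers (main route).* The waiver removes the need for active exudation, for up to 10/20 = 50% of eyes. Section 1.3 reports that mean CPT in the earlier study fell by 67 µm at 24 months. Dry entry is therefore plausible, but no count of dry eyes is given.
- *Other subjects (minor route).* Fluid is one of several alternatives in an angiographic criterion with a 6-month diagnosis window, and Section 3.1 allows prior therapy more than 30 days old. OCT fluid is not literally required. However, the active, leaking and exudative wording makes fluid likely in most of these eyes.
- *Other measures.* Mean thickness and volume changes are averages and do not count eyes that dried. The fundus-photograph grade is per eye and covers subretinal fluid, but it combines fluid with PED, hemorrhage and exudate and is not read on OCT. None gives a per-eye OCT fluid transition.

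**2. How far can the pooled rate lie from the drying rate?**

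Let x = eyes dry at baseline, s = share of those dry at Month 12, and p = drying rate among eyes with baseline fluid. All three are assumptions. From the documents come only the 20 eyes and the ceiling of 10 rollovers.

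Pooled rate = (x·s + (20 − x)·p)/20

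Difference from drying rate = pooled − p = (x/20)(s − p)

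| x | s | p = 0.2 | p = 0.5 |
|---|---|---|---|
| 0 | any | 0 | 0 |
| 1 | 0.8 | 3 points | 1.5 points |
| 3 | 0.8 | 9 points | 4.5 points |
| 5 | 0.8 | 15 points | 7.5 points |
| 5 | 1.0 | 20 points | 12.5 points |
| 10 | 0.8 | 30 points | 15 points |

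The row x = 10 would need, for example, a full rollover quota with every rollover dry at entry. The difference is zero when s = p and negative when s < p: with x = 5, s = 0.4, p = 0.5 it is (5/20)(−0.1) = −2.5 points.

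*Worked example.* Five eyes are dry at baseline and 4 stay dry; 15 have fluid and 6 dry.

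- Pooled: (4 + 6)/20 = 10/20 = 50% (exact 95% CI 27% to 73%).
- Drying rate: 6/15 = 40% (16% to 68%).
- Difference: (5/20)(0.8 − 0.4) = 10 points.

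*The same question from the reader's side.* Suppose the report gives 12/20 = 60% (36% to 81%).

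- x = 0: drying rate 12/20 = 60%.
- x = 5: between (12 − 5)/15 = 7/15 = 47% and 12/15 = 80%.
- x = 10: between (12 − 10)/10 = 2/10 = 20% and 10/10 = 100%.

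The pooled figure does not identify the drying rate unless baseline fluid status is reported with it.

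*Missing scans.* If Month 12 OCTs are missing, 20 is replaced by the number of available eyes where Section 4.8.4 governs. Section 4.8.3 points to the enrolled number instead.

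**The case against.** **The endpoint is coherent as written.** The plan never calls it a drying or resolution rate, and persistent OCT activity is a retreatment criterion in Section 3.1, so staying dry also matters. This stands. It is the reason to keep the pooled rate and add to it.

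**The plan does measure anatomical change from baseline.** This is true of OCT thickness, macular volume and the angiographic and photographic grades. A reader might infer that anatomical response goes unmeasured, and the documents do not support that. The gap is confined to per-eye fluid on OCT.

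**The classification in Section 4.2 already isolates rollovers.** It helps in part. Every rollover has had ranibizumab, so the treatment-naive class contains none. But previously treated eyes may be wet or dry, and Section 4.8.3 commits to no analysis by that class.

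**The size is assumed and the intervals overlap.** Both are correct. In the worked example 27–73% and 16–68% overlap almost entirely. That limits the practical consequence at n = 20 but does not make the two quantities the same.

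**Tempting stronger readings.** A reader might infer that half the eyes enter dry. Ten is a ceiling on rollovers, and the waiver permits inactive disease without implying it. A reader might also infer that many non-rollovers enter dry; the entry wording points the other way. Finally, a reader might infer that the reported rate will overstate drying. That needs both x > 0 and s > p, and the documents establish neither.

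**Conclusion.** The point holds as a limit on interpretation. The Month 12 proportion is a pooled status rate, and the rollover waiver lets eyes dry at entry count as successes. No other planned measure gives a per-eye OCT fluid change. The non-rollover route exists on the wording but is minor.

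The size is (x/20)(s − p). It rests wholly on assumed values and may be zero. Across the values tabulated above it runs from 0 to 30 points, with 7.5 to 15 points at x = 5 and s = 0.8.

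Severity is low. The endpoint is secondary and descriptive in an uncontrolled Phase I study of 20 subjects with no formal sample size calculation. No decision rule depends on it, and the primary safety outcome is unaffected.

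Separately, the Section 4.1.2 bullet "Lesion Characteristics- leaking lesions consistent with PCV" carries no rollover exemption, while Sections 4.1.1 and 4.1.2 waive active exudation for rollovers. These passages must be reconciled. That is a matter of eligibility wording and adds nothing to the severity of the analysis point.

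**What to change.** 1. Keep the pooled proportion and label it a Month 12 status rate.
2. Add a cross-tabulation of baseline against Month 12 OCT fluid, with a count of eyes missing the Month 12 scan.
3. Define the drying rate as eyes with no OCT fluid at Month 12 among eyes with fluid on baseline OCT. Report eyes dry at both visits separately as remained dry, over eyes dry at baseline. Give an exact 95% CI for each.
4. Show the rollover counts in the same table descriptively, since the cells will hold only a few eyes.
5. Reconcile the leaking-lesions bullet with the rollover waiver.

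**Cost.** One definition and one table. OCT is already scheduled at baseline and Month 12 (Section 3.1, Appendix A), so no visit or procedure is added. The price is smaller denominators and wider intervals (6/15: 16% to 68%; 2/10: 2.5% to 56%), and probably a lower headline rate than the pooled one.

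### Leakage area and ICG lesion area have the mean change as their only numerical summary, with no entry limit on lesion size, so in about 20 eyes one or two large lesions can dominate that mean

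*Combined protocol and SAP*

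**What the plan says.** The list of secondary outcome measures in section 3.3 gives each angiographic size outcome one numerical summary. For fluorescein leakage it is "Mean change from baseline in the total area of CNV fluorescein angiographic leakage overtime up to 12 months". For the ICG lesion it is "Mean change from baseline in total area of ICG CNV lesion size (including polyps and deep choroidal vessels) overtime up to 12 months". Neither says whether the change is absolute or relative; absolute is the plain reading.

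The inclusion criteria in section 4.1.2 put no bound on size: "Lesion size- no limitations". The cohort description in section 3.1 sets the number: "Twenty eyes will be treated". Section 4.8.4 uses available cases, so fewer eyes may count at month 12.

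Visual acuity, in the same list, is given two measures of centre: "Median and Average best corrected visual acuity at 4 meters- gain/loss (letters) at 3,6,9,12 months".

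The list also has a non-numerical reading of each angiogram, "graded at each time point compared to baseline as unchanged, resolved, improved, worsened, or cannot determine". For FA and ICG, improvement "will be defined as decreased leakage and/or decreased size, number, or hyperfluorescence of polyps and/or PCV choroidal lesion".

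Section 4.8.3 adds percentages for rates, and one method: "Analysis of Variance will be used to assess for role of variables in for the endpoints". It names no rank-based, transformed or relative summary of area.

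**The concern.** A change in area tends to scale with the starting area: a 20% reduction is 1 mm² in a 5 mm² lesion and 12 mm² in a 60 mm² lesion. In a mean of absolute changes, an eye therefore counts roughly in proportion to its baseline lesion size. With no size limit and about 20 eyes, the mean can describe the largest one or two lesions instead of the typical eye. Acuity has a bounded scale and gets a median as well as a mean. The areas have no upper bound and get the mean alone.

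At stake is the reading of lesion response. Section 1.3 justifies the higher dose partly because limited data suggest that these lesions resist standard-dose monotherapy. The two areas are the plan's direct numerical measures of angiographic lesion response, and section 4.8.1 allows for a later phase II trial. A mean driven by one eye would be a poor guide to such a trial.

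**Working it through.** The plan has no figure to reproduce. Section 4.8.1 makes no sample size calculation, and the documents give no lesion area, SD or distribution. Two checks follow. The first is exact; the second rests on assumptions.

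**1. Break-even of the mean.** Let n − k eyes each shrink by s and k eyes each grow by g. The mean change is zero or positive when g ≥ s(n − k)/k.

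- n = 20, k = 1: g ≥ 19s.
- n = 20, k = 2: g ≥ 9s.
- n = 14 (illustrating missing eyes): 13s for one eye, 6s for two.

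If each large lesion is R times the typical size and the other eyes shrink by a fraction p, the growth each large lesion needs is p(n − k)/(kR). For R = 10 and n = 20:

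| Other eyes shrink by | Growth needed, one large lesion | Growth needed, two large lesions |
|---|---|---|
| 10% | 19% | 9% |
| 20% | 38% | 18% |
| 30% | 57% | 27% |
| 50% | 95% | 45% |

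As an illustration only, let 19 eyes of 5 mm² shrink 20% and one eye of 60 mm² grow 40%. The mean is (19 × 5 × (−0.2) + 60 × 0.4)/20 = (−19 + 24)/20 = +0.25 mm². The median is −1.0 mm².

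**2. Simulation (all inputs assumed).** Twenty eyes per trial; baseline area B lognormal with log-SD 0.8, 1.0 or 1.2 (CV = √(exp(SD²) − 1), about 95% to 180%); follow-up/baseline ratio r lognormal with median 0.8 and log-SD 0.4, independent of B; change = B(r − 1). The expected ratio is 0.8 × exp(0.4²/2) = 0.87, so the true mean change is negative in every setting, and a positive mean is sampling variation.

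| | Equal sizes | log-SD 0.8 | log-SD 1.0 | log-SD 1.2 |
|---|---|---|---|---|
| Mean positive, median negative | 4% | 9% | 11% | 13% |
| 95% t interval for the mean excludes zero | 41% | 31% | 27% | 22% |

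Across the three unequal settings:

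- The two largest lesions supply 28% to 39% of the total absolute change.
- Dropping the single largest lesion flips the sign of the mean in 9% to 13% of trials.
- A signed-rank interval excludes zero in about 43% to 48% of trials, on absolute or percentage change.

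The mean and the signed-rank centre are different quantities, so these rates compare how clearly each summary shows a change. They are not the power of two tests of one hypothesis.

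**Sensitivity.** With baseline log-SD from 0.5 to 1.2, geometric mean ratio 0.7 or 0.8, and ratio log-SD 0.4 or 0.6, the chance of a positive mean with a negative median runs from 0.4% to 29%.

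**The case against.** The strongest reply is that the plan already has a summary that is not weighted by size. Each FA and ICG is graded against baseline at each time point, and each eye counts once. In the illustration, the grades could show about 19 of 20 eyes improved beside a positive mean, and a careful reader would notice. This largely stands on direction. It does not supply a size estimate: an eye whose polyps are less hyperfluorescent but whose area is unchanged can be graded improved, and no amount is attached.

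Second, a reader might infer that reversal is likely. The documents do not support that. They contain no lesion-size data, and having no entry limit does not show that very large lesions will enroll. A large lesion that shrinks with the rest does not change the sign. About 4 points of the simulated 9% to 13% arise even with equal lesion sizes, because changes are skewed. Most reversals are mild: a positive mean with at least 15 of 20 eyes shrinking occurs in about 1% to 2.5% of trials. The 19-of-20 illustration almost never arises under these assumptions (1 of 120,000 simulated trials).

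Third, a reader might infer that the trial's conclusions are at risk. They are not. The primary outcome is adverse events, no test of area change is specified, ANOVA is named only for the role of explanatory variables, and no stated decision depends on these means. Nothing stops the investigators from adding a median. All of this stands, and it limits the weight of the point.

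**Conclusion.** The point holds in a limited form. The mean is the only numerical summary named for the two areas, its scale is unstated, and with about 20 eyes and no size limit it can be dominated, and its sign reversed, by one or two large lesions. That vulnerability follows from the arithmetic and, on the absolute scale, needs no distributional assumption.

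Its frequency does need assumptions. Under the main ones, reversal relative to the median occurs in about 9% to 13% of trials, against 4% with equal lesions. The interval for the mean excludes no change in about 31% to 22%, against about 43% to 48% for a signed-rank interval. Other plausible inputs move the reversal rate widely, so it should be treated as unknown. The effect is on the interpretation of secondary, descriptive outcomes. The change is worth considering because it is nearly free; the safety objective does not depend on it.

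**What to change.** In the secondary outcome measures, for FA leakage area and ICG lesion area:

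- State the scale of the change.
- Report the median and quartiles of each eye's absolute change and percentage change from baseline, each with a signed-rank (Hodges-Lehmann) 95% interval. Count an area of zero at follow-up as −100%.
- Keep the mean and the categorical grades beside them.
- List eyes with zero baseline area separately.

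The last item matters because up to 10 eyes from the previous study may enter without active exudation (sections 3.1 and 4.1.1), so some baseline leakage areas may be zero. Percentage change is undefined for those eyes, though their absolute change still counts. A log-ratio summary alone would not serve, since it also fails for eyes whose area falls to zero.

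The cost is a few sentences and slightly more analysis. No new measurement is needed.
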